2.1 Data analysis general information

Data will be analyzed by Novartis according to the data analysis Section 9 of the study protocol. Important information is given in the following sections and details are provided, as applicable, in Appendix 16.1.9 of the CSR. SAS Version 9.4 or higher will be used to perform all the statistical analyses in the report.

Unless otherwise stated, summary tables/figures/listings will be on all subjects included in the population under consideration.

In general, for continuous data, mean, standard deviation, median, lower quartile, upper quartile, minimum, and maximum will be presented. Categorical data will be presented as frequencies and percentages of patients in each category. For categorical variable summaries, an additional category 'Missing' will be presented if there are missing values for that variable.

If not otherwise specified, p-values will be presented for two-sided hypothesis testing and two-sided confidence intervals will be displayed; the level of significance will be 5% unless otherwise stated.

2.1.1 General definitions

Baseline (Week 0) for Week 24 analysis and overall analysis including both Epoch 3 and Epoch 4 data will be defined as the last measurement before or at the randomization visit. Baseline for End of study analysis including Epoch 4 data only will be defined as the last measurement in Epoch 3.

The first day of administration of randomized study treatment (first dose) is defined as Day 1 for the study. If the date of first administration is missing, then randomization date will be used as Day 1.

All other study days will be labeled relative to Day 1. For event dates on or after Day 1, study day for a particular event date is calculated as [Date of event] – [Date of first dose] + 1. For the dates before Day 1, study day for an event date is calculated as [Date of event] – [Date of first dose]. Duration of an event will be calculated as [Event end date] – [Event start date] + 1. The descriptor “Day 0” will not be used.

For Week 24 analysis, the treatment groups presented are:

- LIK066 2.5 mg qd
- LIK066 10 mg qd
- LIK066 50 mg qd
- LIK066 150 mg qd
- LIK066 2.5 mg bid
- LIK066 5 mg bid
- LIK066 25 mg bid
- LIK066 50 mg bid
- Placebo
- Total (if applicable)

For End of study analysis, unless specified otherwise, the following treatment grouping strategy will be used, expressed as per the Epoch 3 treatment/Epoch 4 treatments a subject is assigned to at randomization:

- LIK066 qd any dose/LIK066 25 mg qd, shortened as LIK066 qd/LIK066 25 mg qd
- LIK066 bid any dose/LIK066 35 mg qd, shortened as LIK066 bid/LIK066 35 mg qd
- Placebo/LIK066 25 mg qd
- Placebo/placebo, shortened as Placebo
- Total (if applicable)

For End of study AE listings, the 10 randomized treatments will be used, as shown in Section 1.1 study design, along with the additional two pooled groups:

- LIK066 qd any dose/LIK066 25 mg qd, shortened as LIK066 qd/LIK066 25 mg qd
- LIK066 bid any dose/LIK066 35 mg qd, shortened as LIK066 bid/LIK066 35 mg qd
- Total (if applicable)

For overall analysis including both Epoch 3 and Epoch 4 treatment, the 10 randomized treatment grouping strategy will be used, as shown in Section 1.1 Study design.

For the Week 24 analyses, data collected up to the end date of Epoch 3 will be included. For AEs and concomitant medications, this means that events with start dates prior to the end of Epoch 3 dates are included.

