## Glossary of terms

Baseline (BL)	Randomization (Visit 201) will be considered BL in this study.
Dosage	Dose of the study treatment given to the subject in a time unit (eg 25 mg once a day, 50 mg twice a day (bid),...).
Electronic data capture (EDC)	EDC is the electronic acquisition of clinical study data using data collection systems, such as Web-based applications, interactive voice response systems and clinical laboratory interfaces. EDC includes the use of electronic case report forms (eCRFs) which are used to capture data transcribed from primary sources used at the point of care.
End of study analysis	Statistical analyses performed at the end of the study including those specified in the statistical analysis plan and any data driven analyses that are performed at study end. The end of study analysis will take place after the last subject has completed Epoch 4 at Week 48.
Enrollment	Time of subject entry into the study at which the informed consent must be obtained (eg prior to starting any of the procedures described in the protocol). In this protocol, this will be at Visit 1 in Epoch 1.
Epoch	A portion of the study which serves a specific purpose. In this study, the 4 epochs are: screening, run-in, randomization & treatment, and follow-up.
eSource	eSource direct data entry refers to the capture of clinical study data electronically, at the point of care. eSource platform/applications reduce the use of paper capture source data during clinical visits. eSource combines source documents and case report forms into one application, allowing for the real time collection of clinical study information to sponsors and other oversight authorities, as appropriate.
Investigational drug	The drug of which the properties are being tested in the study; this definition is consistent with United States code of federal regulations (CFR) 21 Section 312.3 and is synonymous with “investigational new drug” or “investigational medicinal product”. In this study, the investigational drug is LIK066.
Medication pack number	A unique identifier on the label of each investigational drug package.
Randomization number	A unique identifier assigned to each randomized subject, corresponding to a specific treatment arm assignment (see Section 5.3 ).

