### **9.5.1.2 End of study analysis**

A repeated measure ANCOVA model with treatment, visit, the stratification factor, pooled center or region, and treatment by visit interaction as fixed-effect factors and BL as a covariate, and a common unstructured covariance matrix among visits between treatment will be performed separately for the changes from Week 24 to study end in each efficacy variable (body weight, FPG, HbA1c, SBP, DBP, lipid parameters, hsCRP, 24-h UGE and waist circumference). The adjusted mean changes from Week 24 to Week 48 within each treatment, the differences in mean changes from Week 24 to Week 48 between the LIK066 and placebo treatments, and their 95 % confidence intervals obtained from the above models will be presented. The analysis is based on likelihood method with an assumption of MAR for missing data.

A similar repeated measure ANCOVA model with additional glycemic stratification factor by treatment interaction and treatment by visit by stratification factor interaction terms will be performed to assess the body weight change from Week 24 to study end across each of the subgroups (normoglycemic subjects, dysglycemic subjects and subjects with T2DM). The p-value for the interaction of treatment by stratification factor at Week 24 will be calculated from this model as well.

Note that for lipid parameters, the percent changes (instead of absolute change) from Week 24 to study end will be used as a response variable in the above repeated measure ANCOVA model.

Summaries of absolute values and changes (and/or percent changes for body weight and lipid parameters) from Week 24 by treatment group and visit will be presented for all efficacy variables, for all subjects and by stratification strata, respectively. Changes from BL will be similarly summarized as well. Figures will be produced to visually show the raw mean changes by visit over entire study period of 48 weeks for each treatment group.

All analyses will be performed in subjects in the FAS who enter Epoch 4.

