2.7.2.2 End of study analysis

All analyses will be performed in subjects in the FAS who enter Epoch 4.

A repeated measure ANCOVA model with treatment, visit, pooled center or region, and treatment by visit interaction as fixed-effect factors, BL and BL by visit interaction as covariates, and a common unstructured covariance matrix among visits between treatment will be performed separately for the changes from Week 24 to study end in each efficacy variable (body weight, FPG, HbA1c, SBP, DBP, lipid parameters, hsCRP in \log_{10} transformation, 24-h UGE and waist circumference). The adjusted mean changes from Week 24 to Week 48 within each treatment, the differences in mean changes from Week 24 to Week 48 between the LIK066 and placebo treatments, and their 95% confidence intervals obtained from the above models will be presented. The analysis is based on likelihood method with an assumption of MAR for missing data.

Note that for lipid parameters and hsCRP in \log_{10} transformation, the percent changes (instead of absolute change) from Week 24 to study end will be used as a response variable in the above repeated measure ANCOVA model. For HbA1c and FPG, the repeated measure ANCOVA will be fitted for each stratum (normoglycemic, dysglycemic, and T2DM); and for 24-h UGE, the repeated measure ANCOVA will be fitted for both overall population and for each stratum.

Summaries of absolute values and changes (and/or percent changes for body weight and lipid parameters) from Week 24 by treatment group and visit will be presented for all efficacy variables, for all subjects, and by stratification strata if applicable.

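### The SAP's end-of-study model adjusts for the Week 24 value rather than the protocol's randomisation value, which shifts the reported LIK066-placebo differences towards the Week 24 effect

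*SAP*

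**What the plan says.** **Protocol.** The Glossary defines baseline for the whole study: "Randomization (Visit 201) will be considered BL in this study". Section 9.5.1.2 takes change from Week 24 as the response and adjusts for "pooled center or region, and treatment by visit interaction as fixed-effect factors and BL as a covariate". The same section presents summaries relative to Week 24 and then adds: "Changes from BL will be similarly summarized as well". BL there is therefore something other than Week 24.

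**SAP.** Section 2.1.1 keeps the randomisation baseline for the Week 24 analysis and for analyses spanning both epochs. For the rest it states: "Baseline for End of study analysis including Epoch 4 data only will be defined as the last measurement in Epoch 3". Section 2.7.2.2 keeps change from Week 24 as the response and uses "BL and BL by visit interaction as covariates". The quantity to be reported is "the differences in mean changes from Week 24 to Week 48 between the LIK066 and placebo treatments", with 95% confidence intervals. On population: "All analyses will be performed in subjects in the FAS who enter Epoch 4".

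**Record of the change.** The SAP document history has a row dated 25 September 2017 saying that baselines were defined separately for the Epoch 3 and Epoch 4 analyses. SAP Section 4, on changes to protocol-specified analyses, lists only the hsCRP change.

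**The concern.** Epoch 3 and Epoch 4 treatments are assigned together at Visit 201, so the randomised comparison is between whole sequences. The last Epoch 3 value is then a post-randomisation outcome. In the LIK066 arms it has been moved by 24 weeks of drug; in the placebo arm it has not. Adjusting for it compares the arms at a common Week 24 value that is not the mean of either.

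Secondary objective 4 asks what happens to weight and the other efficacy variables between Week 24 and Week 48, after all active subjects move to 25 or 35 mg qd. A method that tilts this contrast in the direction of the Week 24 effect makes persistence look like further improvement, and makes partial loss look like persistence.

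**Working it through.** The documents state no figure for this model, so there is none to reproduce.

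**1. Formula.** Let D be the change from Week 24 to Week 48. With complete data and a covariate-by-visit term, the Week 48 contrast is an ANCOVA of D on the covariate. The within-arm slope of D on the Week 24 value is β − 1, where β = ρ × SD48/SD24. Hence

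adjusted difference = (difference in mean D) − (β − 1) × gap = (difference in mean D) + (1 − β) × gap,

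where gap is the LIK066-minus-placebo difference in Week 24 means. With the Visit 201 value as covariate the corresponding gap is zero in expectation under randomisation, and the extra term drops out.

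**2. Consequence.** If the difference in mean D is zero, the model returns (1 − β) × gap. Conversely, if LIK066 loses a fraction (1 − β) of its Week 24 effect, the model returns zero. For example, with gap −5 mmHg and β = 0.5, a true relative rebound of +2.5 gives 2.5 + 0.5 × (−5) = 0.

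**3. Group sizes.** The ratio has 12 parts, so one part is 432/12 = 36. The qd and bid pools are 36 × 5 = 180 each, and placebo/placebo and placebo/25 mg are 36 each. Applying the 15% loss from protocol 9.8 (used here as an assumption about entry to Epoch 4) gives 153, 153, 31 and 31. About a third are T2DM: 51 versus 10. For the PK substudy of about 120: 120 × 180/432 × 0.85 ≈ 42 versus 120 × 36/432 × 0.85 ≈ 8.

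**4. Check in SD units.** 1,000 simulated trials per setting, 153/153/31/31, zero mean change after Week 24 in every arm, equal SDs so that β = ρ. The last column is how often a two-sided 5% test of a LIK066/LIK066 group against placebo is significant.

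| Gap (SD) | ρ | (1 − ρ) × gap | Simulated | Significant |
|---|---|---|---|---|
| −0.3 | 0.9 | −0.03 | −0.035 | 7% |
| −0.5 | 0.7 | −0.15 | −0.147 | 17% |
| −1.0 | 0.7 | −0.30 | −0.296 | 52% |

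With the Visit 201 covariate all simulated differences for these groups were within 0.01 SD of zero, with rejection of about 4–7%. Placebo/25 mg versus placebo/placebo stayed at about zero under either covariate, because both groups took placebo in Epoch 3.

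**5. Body weight** (assumed SD 20 kg, gap −2.5 to −5 kg, ρ 0.95 to 0.99). The shift runs from 0.01 × (−2.5) = −0.025 kg to 0.05 × (−5) = −0.25 kg. At ρ = 0.95 the SE is about 20 × √(1 − 0.95²) × √(1/153 + 1/31) ≈ 1.23 kg, so the largest shift is about 0.2 SE. Rejection stays near 5%.

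**6. Other variables, illustrative.** Gaps, correlations and SDs are all assumptions. SE = SD × √(1 − ρ²) × √(1/n1 + 1/n0 + g²/(N − 3)), with g the gap in SDs and N = n1 + n0. The last column is the normal approximation from the shift/SE ratio.

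| Variable (n) | Gap, ρ, SD | Shift | SE | Shift/SE | Significant |
|---|---|---|---|---|---|
| HbA1c, T2DM (51 v 10) | −0.5, 0.8, 1.0 | −0.10 | 0.21 | 0.5 | 8% |
| HbA1c, T2DM | −0.8, 0.7, 1.0 | −0.24 | 0.26 | 0.9 | 15% |
| SBP, mmHg (153 v 31) | −3, 0.6, 12 | −1.2 | 1.9 | 0.6 | 10% |
| SBP, mmHg | −5, 0.5, 12 | −2.5 | 2.1 | 1.2 | 23% |
| FPG, T2DM, mg/dL (51 v 10) | −20, 0.6, 35 | −8 | 9.9 | 0.8 | 13% |
| 24-h UGE, g/day (42 v 8) | +40, 0.8, 20 | +8 | 5.8 | 1.4 | 28% |
| 24-h UGE, g/day | +60, 0.6, 25 | +24 | 10.4 | 2.3 | 63% |

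Simulated trials at these gaps and correlations (4,000 per setting) agree: 8–18% for HbA1c, 10–23% for SBP, 13% for FPG, 27–62% for UGE. With the Visit 201 covariate all differences were zero within simulation error, with rejection of 5–6%.

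**7. Sensitivity to β.** Take gap −0.6, SD24 = 1 and ρ = 0.75. An SD48/SD24 ratio of 1 gives β = 0.75 and a shift of −0.15. A ratio of 1.1 gives β = 0.825 and −0.105. A ratio of 1.33 gives β ≈ 1 and no shift.

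**The case against.** **Comparing arms at equal Week 24 values is a recognised analysis.** It is, and it answers a coherent conditional question. But SAP 2.7.2.2 says it will report differences in mean changes, and when the arms differ at Week 24 the conditional contrast is a different quantity. The SAP does not state the conditioning.

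**The change is on record.** The history row of 25 September 2017 shows that the epoch-specific baselines were deliberate. A reader might infer from Section 4 that the change was concealed; the documents do not support that. What stands is that Section 4 omits a departure from the protocol.

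**Non-zero differences need more than a flat trajectory.** A reader might infer a spurious effect whenever nothing changes, or whenever repeat measures are imperfectly correlated. Neither holds. If every subject's value is identical at both weeks, β is 1 and the difference is exactly zero. If the SD grows enough between visits, the shift can vanish (step 7). The condition is no mean change together with β below 1, which is what ordinary within-subject variation with roughly stable SDs gives.

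**The Visit 201 covariate is not a complete cure.** Subjects entering Epoch 4 are selected after randomisation. In the step 7 case with equal SDs, dropout of 50–100% of subjects with high Week 24 values left a bias of −0.04 to −0.08 with the Visit 201 covariate, against about −0.15 with the SAP covariate. This is smaller but not zero.

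**The stakes are limited.** These are secondary variables, the SAP has no key secondary objective, and Section 2.7.2.2 promises estimates and intervals rather than a decision rule. Unadjusted values and changes from Week 24 will also be summarised by group, so a real rebound would remain visible there. The assumed gaps may also be generous: each pool includes low-dose arms, which would shrink the pooled Week 24 difference.

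**Conclusion.** The concern holds in a bounded form. The protocol and SAP specify different covariates for the same response, and the SAP's choice adds (1 − β) × (Week 24 gap) to the contrast for LIK066 qd/25 mg and LIK066 bid/35 mg against placebo/placebo. The direction needs only β below 1 and a Week 24 gap. The sizes for HbA1c, FPG and SBP (about 0.5 to 1.2 SE) and for UGE (about 1.4 to 2.3 SE) are illustrative, since the documents give no SDs, correlations or expected gaps for these variables.

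A reader might infer that the weight results or the primary analysis are compromised. They are not: the Week 24 analysis keeps the randomisation baseline, and the end-of-study shift for weight is at most about 0.2 SE in the settings tried. The comparison of the two groups that took placebo in Epoch 3 is also unaffected. The point merits correction, because it bears on whether effects persist after the dose switch, but it does not threaten the trial's main conclusion.

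**What to change.** In SAP 2.7.2.2, name the Visit 201 value and its interaction with visit as the covariates, and keep change from Week 24 as the response. This restores the protocol's covariate; the visit interaction is the SAP's own addition and can stay.

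If a comparison adjusted for the Week 24 value is also wanted, either restrict it to placebo/LIK066 25 mg versus placebo/placebo, or label it explicitly as conditional on the Week 24 value. List it in SAP Section 4 in either case.

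**Cost.** A wording change and one covariate already collected. Precision falls somewhat: if the Visit 201 value is equally correlated with Weeks 24 and 48, the SE ratio is about √(2/(1 + ρ)), which is 1.05 at ρ = 0.8 and 1.15 at ρ = 0.5, before allowing for the SAP model's own loss from the covariate gap. In simulation the SE rose by about 3–14% for HbA1c, FPG and SBP, and fell by about 16% for UGE, where the large Week 24 gap inflates the SAP model's SE. Selection into Epoch 4 remains under either covariate and should be acknowledged when the results are reported.

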2.2 Analysis sets

Screened set (SCR): the SCR consists of all subjects who signed the ICF.

Randomized set (RAN): All subjects who have received a randomization number, regardless of receiving trial medication.

Run-in set (RUN): All subjects who enter the run-in epoch.

Full analysis set (FAS): the FAS comprises all subjects to whom study treatment has been assigned, except those who are not qualified for randomization but were inadvertently randomized into the study and did not take any study drug. Following the intent-to-treat principle, subjects will be analyzed according to the treatment assigned to at randomization.

Safety set (SAF): the SAF includes all subjects who received at least one dose of study medication. Subjects will be analyzed according to treatment received. Note that the safety set allows the inclusion of non-randomized subjects who received the study drug in error.

Per-protocol set (PPS): the PPS is a subset of the FAS. It consists of all randomized subjects in the FAS who have been exposed to study medication for at least 22 weeks and have no major protocol deviations (PDs) affecting the primary endpoint analysis.

Randomized set – Epoch 4 (RAN-Epoch 4): all randomized subjects who have been assigned a treatment in Epoch 4.

Full analysis set – Epoch 4 (FAS-Epoch 4): all RAN-Epoch 4 subjects, excluding those who did not take any Epoch 4 study medication.

Safety set – Epoch 4 (SAF-Epoch 4): all SAF subjects who received at least one dose of Epoch 4 study medication.

Protocol deviations will be pre-specified prior to un-blinding treatment codes for analyses. See Appendix Table 5-2 and Table 5-3 for list of protocol deviations and criteria that lead to exclusion from analysis sets, and related rules of exclusion criteria of analysis sets.

2.2.1 Subgroup of interest

Subgroups of interest include:

- Glycemic status (dysglycemic, normoglycemic, and T2DM)
- Age ($<65, \geq 65$)
- Sex (Male, Female)
- BMI ($<30, \geq 30; <35, \geq 35$)
- Region (North America, Europe)

Table 2-1 provides an overview of how subgroups are defined/derived and what type of analyses may be performed. Details are specified in relevant sections below.

Table 2-1 Specification of subgroups

Subgroup	Method of derivation	Disposition/ Background & Demographics / Exposure	Efficacy	Safety
Glycemic status (dysglycemic, normoglycemic, and T2DM)	Screening	X	X	X
Age groups: (<65, ≥65 years)	Screening (derived)		X	X
Sex (Male/Female)	Screening		X	X
BMI (<30, ≥30; <35, ≥35)	Baseline		X	
Region (North America, Europe)*	Screening (pooled countries)		X	

* North America: USA and Canada; Europe: Austria, Czech Republic, Hungary, Slovakia and United Kingdom.

2.3 Patient disposition, demographics and other baseline characteristics

2.3.1 Demographics and other baseline characteristics

Week 24 analysis

Demographics, BL characteristics, disease history and medical history will be summarized overall (total) and by treatment group for the FAS. Descriptive statistics (mean, Q1, median, Q3, standard deviation, minimum and maximum) will be presented for continuous variables for each treatment group and for all subjects (total). The number and percentage of subjects in each category will be presented for categorical variables for each treatment group and all subjects (total). Demographics and BL characteristics will be similarly summarized by the stratification factor (glycemic status at screening) as well.

Continuous variables:

- Age
- Height
- Weight
- Body mass index (BMI)
- Waist circumference (cm)
- Smoking pack years
- Baseline pulse (bpm)
- Baseline systolic blood pressure (mmHg)
- Baseline diastolic blood pressure (mmHg)
- Baseline HbA1c (%)
- Baseline FPG (mg/dL)

- Baseline eGFR MDRD mL/min/1.73m²

Categorical variables

- Age category (< 65, \geq 65)
- Gender
- Subjects of child bearing status (females only)
- Race
- Ethnicity
- Smoking status at baseline
- Alcohol history (0, 1, 2, \geq 3 drinks/day)
- BMI (<30, \geq 30; <35, \geq 35)
- Glycemic status (dysglycemic, normoglycemic, and T2DM)
- Baseline HbA1c category (<6.5, \geq 6.5 - < 8%, \geq 8%)
- Baseline eGFR MDRD category (<60, \geq 60 mL/min/1.73m²)

BMI will be calculated using the following formula:

$$\text{BMI} = (\text{body weight in kilograms}) / (\text{height in meters})^2$$

For BMI, the last value of height and body weight prior to randomization will be used.

Medical history will be coded with the medical dictionary for regulatory activities terminology (MedDRA) using the most recent version at the time of database lock. The number and percentage of subjects with each medical condition will be provided by treatment group, primary system organ class, and preferred term.

The protocol solicited medical history events (hypertension, dyslipidemia, prediabetes, sleep apnea, type II diabetes, bariatric surgery, lactic acidosis, urinary tract infection, myocardial infarction, stroke and unstable angina) will be summarized by event type, event status (yes, no, unknown), and treatment.

End of study analysis

Demographics and other BL characteristics including medical history will be similarly summarized for FAS subjects who enter the study Week 24 to Week 48 period (Epoch 4) as for the Week 24 analysis.

